#### 4.1.1 Single dose

A total of 24 healthy subjects from both sexes are planned to be included in the study distributed as follows:

Cohort 1 (0.5 mg B-OT): 3 subjects

Cohort 2 (1 mg B-OT): 3 subjects

Cohort 3 (TBD mg B-OT): 6 subjects

Cohort 4 (TBD mg B-OT): 6 subjects

Cohort 5 (TBD mg B-OT): 6 subjects.

Each cohort starts with a sentinel subject (eligible subject 1). Subjects eligible 2 - 3 or 2 - 6 of the same cohort start treatment after a minimum of 48 hours if safety data indicate that dosing of subsequent subjects of this cohort is justified. Dose escalation to the next dose level occurs if three (first and second cohort) or six subjects (3 next cohorts) have completed the single dose treatment and if PK at Day 2 as well as safety data allow an escalation to the next dose level.

#### 4.1.2 Multiple dose

A total of 24 subjects will be enrolled in the MAD part of the study and assigned to multiple ascending dose groups in consecutive order, in each group 6 volunteers will be included:

Group 1 (1 mg B-OT): 6 subjects

Group 2 (2 mg B-OT): 6 subjects

Group 3 (3 mg B-OT): 6 subjects

Group 4 (5 mg B-OT): 6 subjects.

Each cohort will start with a sentinel subject (subject 1). Subject 2 - 6 of the same cohort will start treatment after a minimum of 72 hours if safety data indicate that dosing of subsequent subjects of this cohort is justified. Dose escalation to the next dose level will occur if six subjects have

completed the multiple dose treatment and if PK at Day 5 as well as safety data allow an escalation to the next dose level.

## 4.2 Subject Disposition (SAD and MAD)

The summary of subject disposition will include the number of subjects in each treatment group who are treated and who completed the study. Reasons for discontinuing treatment and/or study will be tabulated. Volunteers withdrawn from the study because of safety reasons or for reasons unrelated to the study medication will not be replaced. The reasons for withdrawal will be recorded. The number of subjects enrolled, treated, and completing treatment will be tabulated and represented graphically.

Subject disposition will be listed by subject.

The following subject data will be summarized:

- Number and percentage of subjects screened,
- Number and percentage of subjects enrolled,
- Number and percentage of subjects completed and,
- Number and percentage of subjects included in safety population,
- Number and percentage of subjects included in PK and PD populations
- Number and percentage of subjects included in statistical analyses.

A subject who completed the study is defined as a subject for whom the last PK blood sample was assessed.

### 4.3 Definition of Sets for Analysis

Data of all subjects participating in the study will be included in the analyses if the data can meaningfully contribute to the objectives of the study. Subjects who do not complete the sampling schedule of 1 or more study periods may be included in the PK population for only the PK parameters that are judged not to be affected by the missing sample(s).

The decision of which subjects will be included in the PK Analysis Set is to be taken before the start of the sample analysis by the bioanalytical facility.

Statistical analysis and data tabulation will be performed for both SAD and MAD parts using the following subject sets.

#### 4.3.1 Safety analysis set (SF)

The safety population will be defined as all subjects who received at least one dose of B-OT and for whom any safety post-dose data are available.

Unless otherwise stated, the safety analysis set will be used for the presentation of all safety analyses. Exposure to IMP will also be presented using the safety analysis set.

The SF set will be used for summaries of safety and other variables (such as, disposition, concomitant medications, etc.), as well as demographics and subject characteristics.

#### 4.3.2 Pharmacokinetic analysis set

Subjects will be allocated to the PK Analysis Set on a per treatment basis. The PK Analysis Set for a treatment will include all subjects who receive one dose of B-OT, do not violate the protocol in a way that may invalidate or bias the results (major protocol deviation) and have sufficient plasma concentration-time profiles complying with the following criteria at Day 1 (SAD/MAD) and at Day 7 (MAD only):

- Do not have an occurrence of vomiting or diarrhoea which renders the plasma concentration profile unreliable (e.g., if vomiting occurs at or before 2 times median  $T_{max}$ );
- Do not use a concomitant medication which renders the plasma concentration profile unreliable; Day 1: Do not have a pre-dose plasma concentration that is greater than 5% of the  $C_{max}$  value. For SAD part, a subject with pre-dose concentration above 5% of the  $C_{max}$  will be excluded from the PK population; in the MAD part, subject's MAD Day 1 profile will be excluded.
- Have at least one evaluable plasma concentration that is preceded by a lower evaluable concentration and followed by a lower evaluable concentration for the calculation of  $C_{max}$ ,  $T_{max}$  and AUCs.

In case of an important protocol deviation or AEs, affected PK data will be excluded from the descriptive statistical analysis. Where all PK data for a subject are impacted, the subject will be excluded from the PK analysis set. The exclusion of any subjects or time points from the calculation of the PK parameters will be documented by the statistician including the reason(s) for exclusion.

#### **4.3.3 Pharmacodynamic analysis set**

The PD analysis set will consist of all subjects in the safety analysis set who received at least one dose of B-OT and who have at least one post-dose values present, with no important protocol deviations thought to impact on the analysis of the PD data.

#### **4.4 Major Protocol Deviations**

Major protocol deviations, if any, will be reported overall and by treatment groups. The volunteers with major deviations may be excluded from the pharmacokinetic analysis if and only if these deviations could affect the pharmacokinetic parameters.

Major protocol deviations will be identified before the study closure. A list of all protocol deviations will be given.

Major protocol deviations, including taking any concomitant medication that may confound study results or having any non-compliance issues raised by the investigator or sponsor will be summarized by treatment groups, if appropriate. Protocol deviations will be summarized and grouped into different categories, such as:

- Protocol entry criteria.
- Forbidden concomitant medications.
- Missing evaluations for relevant endpoints.
- Other protocol deviations occurring during study conduct.

#### **4.5 Definition of Sub-Group Population in Different Analyses**

No sub-group analysis is planned for this study. However, where data suggest, exploratory sub-group analysis may be performed.

## 5. STATISTICAL ANALYSIS – GENERAL CONSIDERATIONS

This section summarizes the statistical principles and methods planned to analyze the data for this clinical study. The statistical methodology below describes the statistical analysis as it is foreseen when the study is being planned. If circumstances should arise during the study rendering these analyses inappropriate, or if in the meantime improved methods of analysis should come to light, different analyses may be made. Any deviations from the statistical methodology, reasons for such deviations and all alternative or additional statistical analyses that may be performed, will be described in the CSR. Such changes to analyses may be written into an abbreviated SAP, if appropriate.

The calculation of pharmacokinetic parameters will be done with current version of WinNonlin® software [1].

All statistical analyses as well TLFs will be conducted with SAS® current version 9.4 [2] using procedures appropriate for each analysis.

All results will be analysed and presented by treatment group and by time where applicable and separate for SAD and MAD parts.

This study is exploratory and not addresses any pre-defined hypotheses. The assessment of safety and tolerability will be performed on the safety analysis set..

Demographic and baseline data will be summarized by treatment (dose level of B-OT) and overall. Pharmacokinetic data will be summarized by dose level of B-OT. Safety and tolerability data will be summarized.

Frequency (number of subjects and percentages) will be presented for each qualitative variable. Descriptive statistics (n, mean, SD, min, median, max) will be calculated for each quantitative variable (unless otherwise stated). Descriptive statistics will only be presented if  $n \geq 3$ . If no subjects have data at a given time point, then only  $n=0$  will be presented. If  $n < 3$ , only the n, minimum and maximum will be presented. The other descriptive statistics will be left blank.

The following rules will apply to any repeated safety assessments occurring within each cohort:

- If the repeated measurement of a specific parameter occurs prior to IMP administration (Day 1), then the last obtained value prior to dosing will be used in the descriptive statistics and in the calculation of changes from baseline.
- If the repeated measurement of a specific parameter occurs after IMP administration (Day 1), then the first (non-missing) value after dosing will be used in descriptive statistics and in the calculation of changes from baseline.

The planned sequence for measurement of multiple assessments at the same time point is described in Section 12.2.1 Blood samples collection.

For safety assessments performed at Screening and the follow-up, the following rules will apply for any repeated assessments:

- If the repeated assessment occurs at Screening the last available value will be used in the summary statistics.
- If the repeated assessment occurs at the Follow-up Visit the first non-missing assessment will be used in the summary statistics.

Any decisions to deviate from the planned analyses described in the protocol and SAP will be documented in the clinical study report. The clinical study report will also provide a detailed explanation for any deviations from the planned analyses.

## 5.1 Hypotheses

Not applicable. This is an exploratory study.

## 5.2 Assessment of statistical assumptions

Not applicable.

## 5.3 Adjustments for covariate

Not applicable.

## 5.4 Multiple comparisons

Not applicable.

## 5.5 Examination of subgroups

There will be no sub-group analysis.

## 5.6 Pooling of Sites

Not applicable. This is a single-site study.

## 5.7 Interim Analyses

There is no formal interim analysis planned in this study.

## 5.8 Time-Points for Analysis

Statistical analysis will be performed at the end of the MAD part of the study and when the database has been locked. However, PK data of the SAD part have been analyzed prior to the start of the MAD part to allow for selecting dose levels for the MAD part.

## 5.9 Methods for Handling Missing, Unused and Spurious Data

All available data will be included in the analyses and will be summarized as far as possible. Unless otherwise specified there will be no substitution of missing data, i.e. missing data will not be replaced, missing data will be handled as 'missing' in the statistical evaluation.

### 5.9.1 Pharmacokinetic data

Concentrations below the Lower Limit of Quantification (LLoQ) will be indicated as Below the Limit of Quantification (BLoQ) on individual results tabulations. For all descriptive statistics, pre-dose BLoQ concentrations will be set to zero (for single dose concentrations). All other BLoQ concentrations will be set to LLoQ/2.

For computation of PK parameters and relevant statistical evaluations:

- i) Zero (0) imputation will be implemented before the first quantifiable concentration;
- ii) LLoQ/2 imputation will be used between quantifiable concentrations, and
- iii) Values will be ignored (i.e. considered as missing) after the last quantifiable concentration.
- iv) Values reported as missing (no sample or no valid analytical result) will be set as such and will not be included in PK and statistical evaluation. If single data points for plasma B-OT or OT concentrations are missing, the AUC parameters will be derived by linear interpolation with regard to the two neighboring non-missing concentrations.
- v) If the actual sampling time is missing, but a valid concentration value has been measured, the scheduled protocol time will be used for the calculation of derived PK. Pre-dose sampling time will be considered as if it had been taken simultaneously with the drug administration (at zero-hour time point).

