The SAD part of the study showed good tolerability and there were no side effects detected after once-daily administration of B-OT at an escalating dose ranging from 0.5 mg to 5 mg.

No B-OT was detected at any dose level in the plasma of the healthy volunteers.

At the maximum dose of 5 mg, the maximum concentration of OT in human plasma was 15.45 ± 3.76 ng/ml. The time to reach the maximum concentration ranged at the different dose between 1.67 ± 0.29 and 2.50 ± 1.18 hours.

Following single administrations of B-OT, the exposure to OT in terms of C_{max} and AUC_{0-t} increased with ascending doses from 0.5 to 5 mg in a slightly over proportional manner.

Further details can be found in the IB.

Study Rationale

This is a FIH clinical study and as such is conducted primarily to obtain information on safety, PK and PD properties of the tested compound. The scientific rationale of the study is based on the information that RNA viruses such as SARS-CoV-2 bring their own RNA polymerase into the cell. However, after infecting the cell and releasing their viral RNA, they depend on precursors necessary for replication of their viral RNA. The virus is dependent on ribose-5-phosphate (R5P) from the host cell as an essential building block for their replication.

The central switch for the regulation of cell cycle and cell proliferation as well as for the sufficient supply of R5P building blocks is provided by transketolase-like 1 (TKTL1) [Li et al., 2019], which therefore represents a good target for antiviral therapy.

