12.4.4 Determination of plasma drug concentrations and measurement of the transketolase activity

The concentration in Plasma of B-OT, OT and potential other Thiamine metabolites derivate will be determined using a validated liquid chromatography tandem mass spectrometry method and will be conducted in accordance with Good Laboratory Practice regulations and guidelines. Methods validation must be completed prior to start of the analysis.

In the SAD part, For each cohort, in preparation of the SRC, the PK analysis is conducted after all Day 2 (T=48hr) are taken. The rest of the PK samples ((T=72 and 168hr) are analysed after all PK samples are collected at the end of the study. In each run, standard and quality control samples will be distributed throughout the batch containing study samples. Samples with concentrations above the ULOQ will be diluted and re-assayed.

In the MAD part, for each cohort, in preparation of the SRC, the PK analysis will be conducted after all Day 5 samples are taken. The rest of the PK samples are analysed after all PK samples are collected at the end of the study. In each run, standard and quality control samples will be distributed throughout the batch containing study samples. Samples with concentrations above the ULOQ will be diluted and re-assayed. As B-OT was not detected in any cohort of the SAD part, the concentration of B-OT will not be assessed in the MAD. Other metabolites (e.g oxythiamine pyrophosphate) of this prodrug might however be assessed from the back up samples if a validated method has been established before the end of the study.

Full details, including the lower (LLOQ) and upper (ULOQ) limits of quantification range, will be provided in a Bioanalytical Plan

Plasma samples of withdrawn subjects should also be analyzed for drug concentrations and pharmacokinetic parameters (providing withdrawal was not due to withdrawal of consent).

Unacceptable values due to analytical reasons will be handled in accordance with the Bioanalytical Plan.

Measurement of the transketolase activity in erythrocytes will be done following the routinely established procedure to perform the analysis in Medical Laboratory Bremen in the SAD part of the study.

In the MAD part of the study transketolase activity measurement will be done according to a validated method established by the responsible laboratory if available.

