### 8.1.3 Dose proportionality (SAD)

Dose-proportionality for PK parameters of OT and B-OT ( $AUC_{0-\infty}$ ,  $AUC_{0-last}$ , and  $C_{max}$ ) will be assessed by the power model [6]. The slope and the associated 90% CI will be reported. For the first 2 low doses where only 3 subjects are enrolled, no dose proportionality will be assessed. The key modelling assumption is that the logarithm of the PK variable is linearly related to logarithm of dose:

$$\log(PK \text{ parameter}) = \alpha + \beta \cdot \log(Dose) .$$

Let  $X_l$  is the lowest dose, and  $X_h$  is the highest dose, respectively. The predicted geometric mean of the highest dose is  $e^{\alpha} X_h^{\beta}$  and that of the lowest dose is  $e^{\alpha} X_l^{\beta}$  .. Dose proportionality may be defined as the ratio  $e^{\alpha} X_h^{\beta} / e^{\alpha} X_l^{\beta} = X_h / X_l$ , which can be rewritten

as:  $\left( \frac{X_h}{X_l} \right)^{\beta-1} = r^{\beta-1}$ , where  $r$  is the ratio of the highest dose to the lowest dose in the study.

Lower and upper limits may be defined as:  $g_l < \nu < g_h$ . This inequality solved for  $\beta$  gives the criterion for proportionality:  $1 + \frac{\ln(g_l)}{\ln(r)} < \nu < 1 + \frac{\ln(g_h)}{\ln(r)}$ .

Dose proportionality would be declared when the  $(1-2\alpha)*100\%$  CI for  $\beta$  lies entirely within the critical region:  $\left( 1 + \frac{\ln(g_l)}{\ln(r)}; 1 + \frac{\ln(g_h)}{\ln(r)} \right)$ .

Consequently, the dose proportionality of a certain exposure measure of the active ingredient for a given drug product can be concluded at the a significance level if the  $100(1-2\alpha)\%$  confidence interval for  $\beta$  is completely contained within critical region.

SAS/REG procedure will be used to estimate the regression coefficient and its 90% CI.

If the power model has failed to converge and the ANOVA has become the primary analysis, dose proportionality will be concluded if 90% confidence intervals for dose normalised Cmax and AUC are contained in the 80 to 125% range of the reference dose.

A reference dose as well as a maximal dose will be fixed by the Sponsor.

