## 8.2.5 Dose proportionality (MAD)

On Day 7, dose-proportionality for PK parameters of OT and B-OT ( $AUC_{0-\tau}$ , and  $C_{\max,ss}$ ) will be assessed by the power model [6]. The slope and the associated 90% CI will be reported. The same approach will be applied as for SAD ([sec.8.1.3](#)).

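### The SAP's BLoQ rule would show undetected B-OT as a constant LLoQ/2 after every SAD dose, and the SAP plans B-OT dose proportionality that cannot be computed

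*SAP*

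**What the plan says.** SAP 5.9.1 has three separate rules for BLoQ values.

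- **Individual tabulations:** such values "will be indicated as Below the Limit of Quantification (BLoQ) on individual results tabulations".
- **Descriptive statistics:** "For all descriptive statistics, pre-dose BLoQ concentrations will be set to zero (for single dose concentrations"), followed by "All other BLoQ concentrations will be set to LLoQ/2".
- **PK parameters:** "Zero (0) imputation will be implemented before the first quantifiable concentration"; LLoQ/2 is used only between quantifiable values, and values after the last quantifiable one are ignored.

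SAP 8.1.1 requires all plasma concentrations to be summarised, with arithmetic and geometric means. The SAD output list includes both kinds of mean plot. Protocol 14.9 names B-OT explicitly for mean and individual SAD figures.

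On the result itself, protocol 6.1 states: "No B-OT was detected at any dose level in the plasma of the healthy volunteers". Protocol 12.4.4 adds that "the concentration of B-OT will not be assessed in the MAD".

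SAP 8.1.3 nevertheless plans "Dose-proportionality for PK parameters of OT and B-OT" for the SAD, as does SAP 2.2. SAP 8.2.5 plans "dose-proportionality for PK parameters of OT and B-OT" on MAD Day 7, while the MAD part of SAP 2.2 names OT alone. Protocol 14.9.1 also names both analytes.

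**The concern.** Substituting LLoQ/2 is a common convention when a few values in a group are censored. Here every B-OT value is censored, so the summaries would report only the assay limit. Because pre-dose is set to zero and post-dose to LLoQ/2, the mean curve would also rise at the first post-dose sample and stay up for a week, which looks like prodrug exposure.

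B-OT pharmacokinetics after single doses is part of a secondary objective. The correct answer is that B-OT was below quantification at every dose and time, and the summary tables and mean plots would not say so. The B-OT slopes promised in the SAP could not be delivered.

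The situation was known when the SAP was written. Version 2.0 is dated November 2022, after protocol version 3.0 of 13 July 2022, which already reports the non-detection.

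**Working it through.** The plan gives no figure of its own for this point, so the check applies the SAP's rules to an all-BLoQ B-OT data set.

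**Inputs**
- SAD post-dose PK times (SAP Table 1): 0.25, 0.5, 0.75, 1, 1.5, 2, 4, 8, 12, 24, 36, 48, 72 and 168 h, which is 14. With one pre-dose sample this makes 15, matching the 15 PK samples in protocol Table 5.
- SAD subjects (protocol 8.1.2): 3 + 3 + 6 + 6 + 6 = 24, at 0.5, 1, 2, 3 and 5 mg.
- B-OT: every value taken as BLoQ (protocol 6.1).
- LLoQ: not given; protocol 12.4.4 defers it to the Bioanalytical Plan.

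**Number of values affected**
- Pre-dose values set to 0: 24 x 1 = 24.
- Post-dose values set to LLoQ/2: 24 x 14 = 336.
- Post-dose summary cells: 14 times x 5 cohorts = 70.

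**What each cell shows.** With n values all equal to c = LLoQ/2:
- arithmetic mean = nc/n = c, and median = min = max = c;
- SD = 0, so CV = 0%;
- geometric mean = exp(ln c) = c.

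The mean curve therefore steps from 0 to LLoQ/2 at 0.25 h and stays flat to 168 h, identically from 0.5 to 5 mg. At pre-dose the geometric mean is undefined, because ln 0 does not exist.

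**Would anything suppress it?** The only suppression rule in SAP section 5 applies when n < 3. The smallest cohort has 3, so with complete sampling full statistics print in all 70 cells.

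**Height of the plateau.** Only the height depends on the LLoQ. For illustration, assumed values of 0.1, 0.5 and 1.0 ng/mL give plateaus of 0.05, 0.25 and 0.5 ng/mL.

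**Comparison with protocol 14.4.** That section uses half the limit for summaries and graphs, with no pre-dose exception. B-OT would then be flat at LLoQ/2 from pre-dose onward. The apparent rise comes from the SAP's exception, and the two documents disagree at pre-dose.

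**Dose proportionality, SAD.** The two lowest doses are left out, leaving 6 + 6 + 6 = 18 subjects at 2, 3 and 5 mg. Under the parameter rule an all-BLoQ profile gives Cmax and AUC of 0 or not calculable. The model is log(parameter) = alpha + beta x log(dose), and log 0 is undefined, so beta cannot be estimated. The ANOVA fallback in SAP 8.1.3 also log-transforms and fails for the same reason. Such a profile also cannot meet the PK-set requirement in SAP 4.3.2 for a concentration with lower evaluable values on both sides.

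**Dose proportionality, MAD Day 7.** B-OT is not assayed, so there are no data. SAP 8.2.5 conflicts with protocol 12.4.4 and with the MAD part of SAP 2.2.

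**The case against.** The strongest case on the other side is that this is a display matter in an exploratory study whose primary objective is descriptive safety. Much of that stands.

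- **Listings keep the truth.** Individual tabulations show BLoQ, and the protocol already states the non-detection. A row with mean, median, minimum and maximum all equal and SD 0, repeated across a tenfold dose range, would alert a careful reader. The result is obscured in the summaries, not lost.
- **Parameters are untouched.** The LLoQ/2 rule for summaries does not enter Cmax, AUC or half-life. B-OT proportionality is therefore not estimable; it would not come out falsely positive.
- **LLoQ/2 is the protocol's own convention** for summaries and graphs. Replacing it everywhere with zero, or suppressing means above some percentage BLoQ, would be a preference and a wider departure from protocol 14.4.
- **The MAD wording in SAP 8.2.5 looks like a leftover**, since SAP 2.2 names only OT.

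A reader might also infer that the rule distorts the late OT curve and mimics a slow terminal phase. The documents do not support this. They give no LLoQ and no count of BLoQ values for OT, and they describe OT as very low only at 0.5 mg, a dose with no MAD cohort. Nor does the zero rule cover every pre-dose sample: it is limited to single-dose concentrations, so BLoQ troughs during repeated dosing become LLoQ/2.

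None of this removes the core. The SAP has no rule for an analyte that is entirely BLoQ, and it schedules B-OT analyses that cannot be run.

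**Conclusion.** The concern holds for B-OT. Applied as written, SAP 5.9.1 makes all 70 post-dose SAD summary cells for B-OT (336 planned values) equal to LLoQ/2 against 0 at pre-dose, and the mean plots show the same artefact. The B-OT dose-proportionality analyses cannot be carried out in either part of the study.

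This assumes that not detected is reported as BLoQ, that one B-OT LLoQ applies throughout the SAD, and that the planned 24 subjects gave complete samples. Missing samples would lower the count without changing the pattern. The SAP does not say how BLoQ is drawn in individual plots; protocol 14.4 would use LLoQ/2 there too.

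The effect is limited to the SAD summary tables and mean plots for one secondary objective and to the B-OT proportionality text. No safety result, escalation decision or PK parameter is shown to depend on it. It should be corrected because the outputs would be wrong and the correction is cheap.

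**What to change.** 1. In SAP 5.9.1, state that where all values of an analyte at a time point are BLoQ, the summary reads BLoQ with the number BLoQ, and no mean, geometric mean or mean curve is produced. B-OT is then listed as BLoQ with no parameters.
2. Delete B-OT from the dose-proportionality text in SAP 2.2 (SAD), 8.1.3 and 8.2.5.
3. Reconcile the pre-dose rule in SAP 5.9.1 with protocol 14.4, and record the departures from protocol 14.4, 14.9 (B-OT mean figures) and 14.9.1 (B-OT proportionality). SAP section 5 already provides for documenting deviations in the study report.
4. Optionally, show the number and percent BLoQ for OT at each time.

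The cost is SAP wording and a small programming change. No new data are needed and fewer outputs are produced. The only downside is that some summary cells read BLoQ instead of a number.
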